9.1 Analysis sets

The following analysis sets will be used for the statistical reporting and analyses:

Enrolled Set: The Enrolled Set consists of all enrolled patients for the initial 16-week, Treatment Period 1.

Responder Set: The Responder Set consists of all patients who are labeled as responders at the end of Treatment Period 1, and enter Treatment Period 2 receiving blinded secukinumab 150 mg every 4 weeks through Week 48.

Randomized Set: The Randomized Set consists of all randomized patients.

Safety Set: The Safety Set includes all patients who received at least one dose of study treatment during Treatment Period 2. Patients will be analyzed according to the study treatment received.

Full Analysis Set: The Full Analysis Set comprises all patients to whom study treatment has been assigned by randomization. Patients inappropriately randomized (e.g., IRT was called in error for randomization of a screen failed patient) will be excluded from this analysis set. According to the intent-to-treat principle, patients will be analyzed according to the treatment they have been assigned to during the randomization procedure.

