## 2.2 Analysis sets

The following analysis sets will be used for the statistical reporting and analyses:

**Enrolled Set:** The Enrolled Set consists of all enrolled patients for the initial 16-week, Treatment Period 1.

Note: For safety analyses, the Enrolled Set will consist of enrolled patients for the initial 16-week, Treatment Period 1 who received at least one dose of the open-label treatment, secukinumab 150 mg.

**Responder Set:** The Responder Set consists of all patients who are labeled as responders at the end of Treatment Period 1, and enter Treatment Period 2 receiving blinded secukinumab 150 mg every 4 weeks through Week 48.

**Safety Set:** The Safety Set includes all patients who received at least one dose of study treatment during Treatment Period 2. Patients will be analyzed according to the study treatment received.

**Full Analysis Set:** The Full Analysis Set comprises all patients to whom study treatment has been assigned by randomization. According to the intent-to-treat principle, patients will be analyzed according to the treatment they have been assigned to during the randomization procedure.

**Non-responder Set:** The Non responder Set consists of all patients who are labeled as non-responders at the end of Treatment Period 1 and do not enter Treatment Period 2.

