### **2.5.3 Handling of missing values/censoring/discontinuations**

Patients who discontinue prematurely for any reason will be considered nonresponders from the time they discontinued through Week 52. Also, patients who do not have the required data to compute response (ASDAS components) at the specific time point will be classified as nonresponders.

In an additional analysis, missing data for ASDAS inactive disease response will be imputed using multiple imputation. Details for multiple imputation is presented in Appendix [Section 5.4](#).

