## 5.5 Rule of exclusion criteria of analysis sets

**Table 5-1 Protocol deviations that cause subjects to be excluded**

Deviation ID	Description of deviation	Exclusion in analyses	Severity code
D01	Patient met one or more of the Discontinuation of Study Drug criteria but study drug was not discontinued	Include in everything	0
D02	Patient voluntarily withdrew consent. However, still continuing in the study.	Exclude from everything	9
E01	Patient enrolled with total ankylosis of the spine	Include in everything	0
E02	Patient used other investigational drugs within 5 half-lives of enrollment, or within 4 weeks before the Baseline Visit, whichever is longer	Include in everything	0
E03	Patient enrolled with history of hypersensitivity to any of the study drugs or its excipients or to drugs of similar chemical classes	Include in everything	0
E04	Patient enrolled with Chest x-ray, CT scan, or chest magnetic resonance imaging (MRI) with evidence of ongoing infectious or malignant process, obtained within 3 months prior to screening and evaluated by a qualified physician	Include in everything	0
E05	Patient enrolled with previous exposure to secukinumab or any other biologic drug directly targeting IL-17, IL-12/23, or the IL-17 receptor, or any other biologic immunomodulating agent, except those targeting TNF $\alpha$	Include in everything	0
E06	Patient who took more than one anti-TNF $\alpha$ agent	Include in everything	0
E07	Patient took any intramuscular or intravenous corticosteroid injection within 2 weeks before baseline	Include in everything	0
E08	Patient took any therapy by intra-articular injections (e.g. corticosteroid) within 4 weeks before baseline	Include in everything	0
E09	Patient enrolled whose previous treatment with any cell-depleting therapies including but not limited to anti-CD20, investigational agents (e.g., CAMPATH, anti-CD4, anti-CD5, anti-CD3, anti-CD19)	Include in everything	0
E10	Patient using high potency opioid analgesics (e.g., methadone, hydromorphone, morphine)	Include in everything	0
E11	Patient enrolled with active systemic infections during the last two weeks	Include in everything	0

Deviation ID	Description of deviation	Exclusion in analyses	Severity code
	(exception: common cold) prior to baseline		
E12	Patient enrolled with active ongoing inflammatory diseases other than AS that might confound the evaluation of the benefit of secukinumab therapy, including inflammatory bowel disease or uveitis	Include in everything	0

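### SAP deviation D02 (consent withdrawn, patient still continuing) removes the patient from all five analysis sets, against the SAP's own definitions of the Full Analysis Set and the Safety Set

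*SAP*

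**What the plan says.** SAP 5.5, Table 5-1, lists protocol deviations and their effect on the analysis sets. D02 reads "Patient voluntarily withdrew consent. However, still continuing in the study". Its consequence is "Exclude from everything", severity code 9. Every other row of the table carries code 0.

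SAP 2.2 defines the sets without any exception for consent:

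- Full Analysis Set: "The Full Analysis Set comprises all patients to whom study treatment has been assigned by randomization". It continues: "According to the intent-to-treat principle, patients will be analyzed according to the treatment they have been assigned to during the randomization procedure".
- Safety Set: "The Safety Set includes all patients who received at least one dose of study treatment during Treatment Period 2".

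The only Full Analysis Set exclusion in protocol 9.1 is for errors in randomisation: "Patients inappropriately randomized (e.g., IRT was called in error for randomization of a screen failed patient) will be excluded from this analysis set".

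For the primary endpoint, SAP 2.5.3 states: "Patients who discontinue prematurely for any reason will be considered nonresponders from the time they discontinued through Week 52". It adds that "patients who do not have the required data to compute response (ASDAS components) at the specific time point will be classified as nonresponders". Protocol 5.6.2 lists withdrawal of informed consent among the circumstances that require discontinuation of treatment and of the trial.

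**The concern.** An exclusion table should put the set definitions into effect, and this row overrides them. A patient who was randomised, dosed and observed under valid consent, and who then withdrew it while trial activity went on, disappears from the denominator of the primary analysis and from the safety tables. A patient who withdrew consent and did stop stays in the Full Analysis Set as a non-responder. The two differ only in what happened after withdrawal.

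Two things are at stake. The first is an exclusion after randomisation from an analysis described as intent-to-treat. The second is the removal of an exposed patient's doses and adverse events from the set-based safety summaries.

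The row is not limited to randomised patients. A case in Treatment Period 1 would leave the Enrolled Set, and a responder would leave the Responder Set.

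**Working it through.** **1. Code trace.** D02 has code 9 (Table 5-1). Table 5-2 lists the codes that exclude a patient from each set:

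- Safety Set: 5, 7, 9
- Full Analysis Set: 4, 7, 8, 9
- Enrolled Set: 1, 9
- Responder Set: 2, 8, 9
- Non-Responder Set: 6, 8, 9

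Code 9 is in 5 of 5 rows, so a D02 patient belongs to no analysis set.

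**2. Against the definitions.** A randomised D02 patient meets the SAP 2.2 definition of the Full Analysis Set. If dosed at Week 16 or later, the patient also meets the definition of the Safety Set. Protocol 9.1 excludes only inappropriate randomisations. SAP Section 4 lists the changes from the protocol (no multiple imputation for the continuous secondary variables, MMRM in place of ANCOVA and LOCF, the Enrolled Set definition for safety, deletion of the Randomized Set). The D02 exclusion is not among them.

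**3. Against neighbouring rows.** D01 covers a patient who met a discontinuation criterion but was not taken off study drug; it is code 0. Withdrawal of consent is itself such a criterion (protocol 5.6.2), so a D02 patient who is still being dosed fits both rows, with opposite results. O02 covers deficient informed consent documentation and is also code 0.

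**4. Against the non-responder rule.** This conflict is indirect. SAP 2.5.3 applies to patients who discontinue, and D02 describes patients who did not. The link is protocol 5.6.2: consent withdrawal requires discontinuation, so the handling consistent with SAP 2.5.3 is non-response from the withdrawal date.

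**5. Size.** First, the plan's own figures, with response rates of 20% and 10% and a half-width of 10 points:

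- n per arm = 1.96² × (0.20×0.80 + 0.10×0.90) / 0.10² = 96.04, rounded up to 97. This reproduces the stated sample size.
- At 97 per arm, SE = √(0.25/97) = 5.08 points and half-width = 9.95 points.

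The documents give no D02 count, so I assume 1 to 5 cases in one arm, each of whom would otherwise count as a non-responder. With whole-number responders nearest the planned rates and everyone kept, 19/97 - 10/97 = 19.59% - 10.31% = 9.28 points (95% CI -0.67 to 19.23, normal approximation; crude odds ratio 2.12).

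| Non-responders removed | From 300 mg only: difference (points) | From 150 mg only: difference (points) |
|---|---|---|
| 1 | 19/96 - 10/97 = 9.48 | 19/97 - 10/96 = 9.17 |
| 3 | 19/94 - 10/97 = 9.90 | 19/97 - 10/94 = 8.95 |
| 5 | 19/92 - 10/97 = 10.34 | 19/97 - 10/92 = 8.72 |

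One removal therefore shifts the difference by +0.20 or -0.11 points. One from each arm gives 9/96 = 9.38 points, a shift of about 0.1. The crude odds ratio with five removed is 2.26 (300 mg arm) or 2.00 (150 mg arm).

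If the removed 300 mg patient would instead have been counted as a responder at Week 52, one removal gives 18/96 - 10/97 = 8.44 points. That comparison applies only if data collected after withdrawal would otherwise have been used.

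**The case against.** The strongest reply is that D02 is a narrow clean-up row for an irregular situation, probably with few or no cases, and that respect for withdrawn consent is reason enough. Several parts of that stand.

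- **Ordinary withdrawals are untouched.** A reader might infer that everyone who withdraws consent leaves the denominator. The text does not say so. D02 needs the patient to be still continuing, and all other withdrawals fall under SAP 2.5.3 as non-responders.
- **Dependence on outcome is not shown.** A reader might infer selection by response or by arm. Nothing in the documents ties a failure to stop to the ASDAS result. Patients, sites and sponsor study staff were blinded until final lock (protocol 5.4). The deviation rules entered the SAP on 01-Apr-2021, before lock, and the post-lock update of 08-Jul-2021 does not list Section 5.5. Dependence is a risk and no more.
- **Adverse events are not lost altogether.** They leave the set-based summaries. They are still captured on the CRF, and SAEs are still reported to the sponsor (protocol 7.2.1 and 7.2.1.1).
- **The documents are silent on data use.** Protocol 5.6.3 does not say whether data collected before withdrawal may be used, and the consent form is a separate document. A consent-based reason cannot be ruled out.

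Consent protection does not explain the table as it stands, however. Deficient consent documentation (O02) is kept in every set, while a patient who gave consent and later withdrew it is erased back to the first dose. If the consent form does require that, the SAP should say so. Leaving out data collected after withdrawal would be a reasonable aim, but code 9 goes well beyond it.

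**Conclusion.** The contradiction between Table 5-1 and SAP 2.2 is plain on the text and should be corrected. It is a stated rule that gives the wrong analysis population, not a missing detail.

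The expected effect on efficacy is small: at most about 0.2 points on the difference per patient who would otherwise be a non-responder, up or down according to arm, against a planned half-width of 10 points. Five such patients, all from one arm, would put the illustrative difference anywhere from 8.72 to 10.34 points. In the 300 mg case the lower confidence limit moves from -0.67 to 0.09. A reader might infer from this that D02 could decide the trial. That does not follow: the count is an assumption, five from one arm is the extreme of the assumed range, and the objective is estimation.

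The reason to act is consistency with intent-to-treat and keeping exposed patients in the safety tables. No sample-size figure changes: with D02 patients kept, the denominators stay at the planned 97 per arm.

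**What to change.** In Table 5-1, change D02 from code 9 to inclusion. That alone is not enough, because code 0 would also bring in data collected after withdrawal and no existing code cuts data at a date. Add a short handling rule to the SAP:

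- Data up to the withdrawal date are used.
- In the Full Analysis Set the patient is a non-responder from that date, for the primary variable and the binary secondary variables (SAP 2.5.3 and 2.7.3).
- Exposure and adverse events up to that date stay in the Safety Set, or in the Enrolled Set for Treatment Period 1. State how this cut-off applies to the 84-day windows in SAP 2.4.1 and 2.8.1.
- Data collected after withdrawal are left out of the summaries, except for the End of Study Visit and the SAE and adverse event follow-up that protocol 5.6.3 provides for.
- Define what still continuing means, so that attending the End of Study Visit does not by itself make a patient D02.

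Report the number of D02 patients by arm. If any tables were produced under code 9 and the count is not zero, show the primary result both ways.

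Cost: one table row, a short handling rule and minor programming. No new data are needed.

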**Table 5-2 Analysis set exclusions based on codes**

Analysis set	Codes that cause a subject to be excluded
SAF	5, 7, 9
FAS	4, 7, 8, 9
ENR	1, 9
Responder Set	2, 8, 9
Non-Responder Set	6, 8, 9

**Table 5-3 Code text**

Code	Code text
0	Include in everything
1	Exclude from Enrolled Set
2	Exclude from Responder Set
3	Exclude from Randomized Set (RAN)
4	Exclude from Full Analysis Set (FAS)
5	Exclude from Safety Set (SAF)
6	Exclude from Nonresponder Set
7	Exclude from FAS and SAF
8	Exclude from FAS, Responder Set, Randomized Set and Nonresponder Set
9	Exclude from everything

## 5.6 Evaluation algorithm for ASDAS inactive disease status

At Week 12 and Week 16, all patients will be assessed for achieving the ASDAS inactive disease (total score < 1.3) status, as well as for an inadequate response or a non-response. Patients will then be divided into three groups in the following order:

- Responders: Patients achieving ASDAS inactive disease (total score < 1.3) at **both** Week 12 and Week 16 and who do achieve a decrease (improvement) from baseline in total ASDAS score at both Week 12 and Week 16.
- Inadequate responders: Patients not achieving ASDAS inactive disease at Week 12 and Week 16 (i.e., not achieving total score < 1.3), but who do achieve decrease (improvement) from baseline in total ASDAS score at Week 12 and Week 16.
- Non-responders: Patients who exhibit no change or an increase (worsening) from baseline in total ASDAS score at **either** Week 12 **or** Week 16.

Patient	Baseline ASDAS	Week 12 ASDAS <1.3	Week 16 ASDAS < 1.3	Week 12 ASDAS < Baseline	Week 16 ASDAS < Baseline	Responder status	Definition
Patient 1		Yes	Yes			Responder	1
Patient 2	?	No	No	Yes	Yes	Inadequate	2
Patient 3	?	Yes	No	Yes	Yes	Inadequate	2
Patient 4	?	No	Yes	Yes	Yes	Inadequate	2
Patient 5	?	No	No	Yes	No	Non-responder	3
Patient 6	?	No	No	No	Yes	Non-responder	3
Patient 7	?	No	No	No	No	Non-responder	3
Patient 8	?	Yes	No	Yes	No	Non-responder	3
Patient 9	?	Yes	No	No	Yes	Non-responder	3
Patient 10	?	Yes	No	No	No	Non-responder	3
Patient 11	?	No	Yes	Yes	No	Non-responder	3
Patient 12	?	No	Yes	No	Yes	Non-responder	3
Patient 13	?	No	Yes	No	No	Non-responder	3

SAS program logic:

Do;

If ASDAS12 < 1.3 and ASDAS16 <1.3

then RESPONSE = "Responder";

Else if ASDAS12 < ASDAS0 and ASDAS16 < ASDAS0

then RESPONSE = "Inadequate";

Else RESPONSE = “Non-responder”;

End;

